8.0 Dosage Modification Based on Adverse Events

Dose modification guidelines are provided specifically for venetoclax, polatuzumab vedotin, rituximab, and rituximab/hyaluronidase human in the tables below. In addition, Venetoclax dose reductions will be discussed in Section 8.21.

If the patient requires a dose reduction, no dose re-escalation (e.g. no return to the baseline dose) is permitted.

Additional dose reductions may be employed at investigator discretion as clinically appropriate to ensure patient safety, and exact modification, timing, and reasons should be recorded.

8.1 Assessment of Safety

The safety plan for patients in this study is based on clinical experience with rituximab, rituximab and hyaluronidase human, polatuzumab vedotin, and venetoclax. The anticipated important safety risks of rituximab, rituximab and hyaluronidase human, polatuzumab vedotin, and venetoclax are outlined below. Please refer to the rituximab, rituximab and hyaluronidase human, polatuzumab vedotin, and venetoclax Investigator's Brochures for a complete summary of safety information.

8.2 Venetoclax Dose Reduction and Re-Escalation Steps

The dose of venetoclax may be reduced. If administration of chemotherapy is delayed, the administration of Pola and R/SC should be delayed for the same timeframe; for example, if polatuzumab and rituximab and hyaluronidase are delayed, administration of venetoclax should also be delayed so that they are given together beginning on Day 1 of the same cycle.

For non-hematologic toxicities, dosing of Pola and R/SC may be resumed upon resolution to Grade 1 or baseline status. Resumption of dosing without complete resolution of toxicity may only be considered after careful weighing of the benefits and risks with the patient. A dose delay of 21 days is permitted for immunochemotherapy to allow recovery of hematologic toxicities to Grade 2 or non-hematologic toxicities to Grade 1 or baseline status for the first episode. Actions for recurrent hematologic adverse events are described in Table 8.31. If treatment is delayed for more than 3 weeks, the patient should be withdrawn from study treatment except in exceptional circumstances which may be discussed with the study chair. (NOTE: Lymphopenia is not considered a cytopenic toxicity, as it is an expected outcome of therapy). Patients who discontinue all study treatment for adverse events should proceed to clinical follow up and remain in the study.

The dose of venetoclax may be reduced according to the following dose reduction steps based on the starting dose.

Table 8.21: Venetoclax Dose Reduction Steps during Induction and Maintenance (Duration of Venetoclax in Maintenance is 1 year).

	Venetoclax Dose Reduction	
Starting Dose	Step 1	Step 2
(Dose 0)	(Dose -1)	(Dose -2)
400 mg	300mg	200mg
(days 1-21)	(days 1-21)	(days 1-21)
300mg	200mg	100mg
(days 1-21)	(days 1-21)	(days 1-21)
200mg	100mg	50mg
(days 1-21)	(days 1-21)	(days 1-21)
100mg	50mg	20mg
(days 1-21)	(days 1-21)	(days 1-21)
50mg (days 1-21)	20mg (days 1-21)	

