8.3 Toxicities during Induction Treatment

Table 8.31: Guidelines for Management of Hematologic Toxicities That Occur During Induction Treatment.

Heatment.					
Event	Action to Be Taken				
Grade 3 or	For patients who have had one or no prior venetoclax or polatuzumab vedotin				
4	dose reduction:				
Hematogic	• Withhold study treatment. ¹				
Toxicity ¹	 Administer RBCs or platelets as required. 				
	 If patient has not already initiated G-CSF, initiate prophylactic G-CSF for current and subsequent cycles. 				
	 Resume venetoclax and polatuzumab vedotin at same dose after interruption for 1st occurrence, once the toxicity has resolved to Grade 1 or baseline level 				
	 Resume venetoclax and polatuzumab vedotin at one level dose reduction after interruption for 2nd occurrence, once the toxicity has resolved to Grade 1 or baseline level. Refer to table 8.21 for dose reduction steps. 				
	• For patients who develop platelet count of 20,000/L while receiving LMWH, reduce the dose of LMWH. For patients who develop platelet count of 20,000/L while receiving platelet inhibitors, consider temporarily withholding platelet inhibitors.				
	No more than 2 dose level reductions in venetoclax and				
	polatuzumab vedotin are allowed during induction.				
	 Consider discontinuation of study drug for patients who require withholding study drug for more than 21 days. 				
	For patients who have had two prior venetoclax dose reductions:				
	 Permanently discontinue study treatment. 				
	 For grade 4 thrombocytopenia ≥ 7 days or grade 3 thrombocytopenia with ≥ grade 2 bleeding resume venetoclax and polatuzumab at one dose level dose reduction after the toxicity has resolved to Grade 1 or baseline level 				

(G-CSF) granulocyte colony-stimulating factor; (LMWH) low molecular weight heparin.

¹ Treatment delays apply to all toxicities; dose modifications apply only to toxicities that are considered to be related to any of the study treatment components. Toxicities that occur during the cycle and subside prior to the next cycle should not trigger the suggested dose modifications.

Table 8.32: Guidelines for Management of Non-Hematologic Toxicities That Occur During Induction

Table 8.32: Guide	elines for Management of Non-Hematologic Toxicities That Occur During Induction		
Event	Action to Be Taken		

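### For Grade 3-4 hematologic toxicity in induction, Section 8.2 and Table 8.31 set different first-episode recovery levels, and Tables 8.31 and 8.51 give different doses after a second event present on Day 1

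*Combined protocol and SAP*

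**What the plan says.** **First episode.** Section 8.2 permits a 21-day delay of immunochemotherapy "to allow recovery of hematologic toxicities to Grade 2" for the first episode. Table 8.31 (Section 8.3) has its own first-occurrence rule: "Resume venetoclax and polatuzumab vedotin at same dose after interruption for 1st occurrence, once the toxicity has resolved to Grade 1 or baseline level".

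**Later episodes.** Section 8.2 adds: "Actions for recurrent hematologic adverse events are described in Table 8.31". That table's rule is: "Resume venetoclax and polatuzumab vedotin at one level dose reduction after interruption for 2nd occurrence", at the same Grade 1 or baseline recovery level. Its footnote 1 narrows this in two ways: "dose modifications apply only to toxicities that are considered to be related to any of the study treatment components", and "Toxicities that occur during the cycle and subside prior to the next cycle should not trigger the suggested dose modifications".

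**Table 8.51 (Section 8.5).** This table is headed as polatuzumab management. Its rows for Grade 3-4 neutropenia and thrombocytopenia, with severity judged on Day 1 of any cycle, hold all treatment until ANC exceeds 1000 or platelets exceed 75,000 per microliter. If that happens by Day 7, all treatment restarts with no further dose reduction.

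**Long holds.** Section 8.2: "If treatment is delayed for more than 3 weeks, the patient should be withdrawn from study treatment except in exceptional circumstances". Table 8.31: "Consider discontinuation of study drug for patients who require withholding study drug for more than 21 days".

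**Permanence.** Section 8.0 bars re-escalation after a reduction. Note 3 to Table 7.3 keeps a venetoclax dose reduced in induction at that level in maintenance.

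**The concern.** Sites treating the same event have two sets of instructions.

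At a first episode the difference is in timing. Both texts leave the dose unchanged, but the hold can last longer under Table 8.31. A patient who reaches Grade 2 and no better within three weeks may restart under 8.2. A site waiting for Grade 1 or baseline runs that patient into the withdrawal limit.

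At a second event present on Day 1 the difference is in dose. A site reading Table 8.31 lowers two drugs and a site reading Table 8.51 lowers neither. Because reductions cannot be undone, similar patients could receive different doses for the rest of treatment depending on which table the site opened.

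**Working it through.** The protocol has no figure of its own to reproduce here. The check is a comparison of texts, followed by simple dose arithmetic.

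**Step 1. First related Grade 3-4 event, recovered to Grade 2 by Day 21, baseline better than Grade 2**

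| Source | Recovery level | Result |
|---|---|---|
| 8.2 | Grade 2 | May resume |
| Table 8.31 | Grade 1 or baseline | Stays on hold |
| 8.2, delay beyond 3 weeks | n/a | Withdrawal by default |
| Table 8.31, hold beyond 21 days | n/a | Consider discontinuation |

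Two possible explanations do not remove the difference:
- Table 8.43 uses Grade 2, but it covers maintenance. The 8.2 text concerns delays of polatuzumab and rituximab, and polatuzumab is not given in maintenance.
- If a comparison sign was lost in the PDF text, Grade 2 or lower still differs from Grade 1 or lower.

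**Step 2. Second related Grade 3-4 neutropenia or thrombocytopenia, present on Day 1, recovered by Day 7**

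Footnote 1 of Table 8.31 exempts unrelated toxicities and those that subside before the next cycle. A related event still present on Day 1 is neither, so the one-level cut applies. Footnote b of Table 8.51 concerns cytopenia caused mainly by lymphoma and does not cover this event. Its rows refer to all treatment, so venetoclax is included despite the heading.

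The example patient meets both tables' recovery levels. It therefore does not depend on converting counts to CTCAE grades, which the documents do not set out.

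**Step 3. Size of the dose difference**

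- Venetoclax, one level in Table 8.21 from 400 mg: (400 − 300) / 400 = 25%.
- If the trial dose has become 300 mg: (300 − 200) / 300 = 33%.
- Polatuzumab: Table 8.31 refers to Table 8.21, which lists venetoclax only. Assuming the step meant is 1.4 mg/kg, the only lower dose named in Section 8 (for neuropathy): (1.8 − 1.4) / 1.8 = 22%.

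**Step 4. Duration for a patient on 400 mg**

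Table 7.2b reaches 400 mg in cycle 2 week 2, so the event is placed on Day 1 of cycle 3, 4, 5 or 6.

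- Induction days left: from cycle 3, 4 × 21 = 84. From cycle 6, 21.
- Maintenance: 12 cycles of 30 days. Table 7.3 gives both Days 1-21 and daily dosing for up to a year. That is 12 × 21 = 252 days, or 12 × 30 = 360 days.

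| Reading of Table 7.3 | Event at cycle 6 | Event at cycle 3 |
|---|---|---|
| Days 1-21 | 21 + 252 = 273 days | 84 + 252 = 336 days |
| Daily | 21 + 360 = 381 days | 84 + 360 = 444 days |

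At 100 mg per day this is 27,300 to 33,600 mg of venetoclax under the first reading and 38,100 to 44,400 mg under the second. Days on hold are not subtracted, and dosing between cycle 6 and the end-of-induction assessment is not counted.

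These totals are not extended to a 300 mg trial dose. The asterisk under Table 7.3 gives a different maintenance fallback (400 mg on Days 1-10) if the starting dose is not tolerated in the safety run-in.

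**The case against.** The best defense has four parts.

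1. **Precedence for recurrent events is largely stated.** Section 8.2 sends them to Table 8.31, which is the induction hematologic table and the only one that separates first from second occurrences. This stands in part. A reader might infer that the protocol leaves second events with no governing rule, and the pointer in 8.2 rules that out. What remains is that Table 8.51 covers the same Day 1 event, places no limit by occurrence and does not defer to Table 8.31. Its exclusion of additional reductions could mean none beyond Table 8.31, but it does not say so.

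2. **The first-episode texts can both be followed.** Section 8.2 permits a delay and does not oblige anyone to restart at Grade 2, so waiting for Grade 1 or baseline breaches nothing. That is correct, and reading 8.2 as mandatory would go too far. But waiting has a cost: a patient whom 8.2 would let resume can pass three weeks and be withdrawn.

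3. **These are guidelines.** Section 8.0 allows additional reductions at the investigator's discretion and requires modifications, timing and reasons to be recorded. Differing practice would therefore be visible in the data. But discretion to reduce further does not say when the Table 8.31 reduction may be skipped.

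4. **The dose case is narrow.** It needs a second, related event, present on Day 1 and recovered by Day 7, after the G-CSF that Table 8.31 starts in patients not already on it. This stands and limits how much weight the totals can bear.

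**Conclusion.** The inconsistency is real and needs correcting. It has two parts: a different recovery level at the first episode, and a different dose after a second related Grade 3-4 neutropenia or thrombocytopenia that is present on Day 1 and recovered by Day 7. It does not extend to anemia, for which Table 8.51 has no row, or to recovery after Day 7, for which those rows give no dose.

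For a patient on 400 mg, venetoclax is 25% lower under Table 8.31, for the duration worked out above. That assumes a CR or PR at the end of induction and completed maintenance. The 22% figure for polatuzumab rests on the assumption that 1.4 mg/kg is the step meant.

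Two stronger inferences are not supported. A reader might take the day totals as an expected effect across the trial, but the documents do not say how often such second events will occur. A reader might also treat the differing language on holds over 21 days as a further contradiction. A site that follows 8.2 satisfies both texts, so that is a difference in firmness only. Nothing here changes the sample size, significance level or power.

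**What to change.** Change the wording of Section 8:

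- State in 8.2 that Table 8.31 governs both first and recurrent hematologic toxicity in induction.
- Replace the Grade 2 recovery level in 8.2 with the Grade 1 or baseline level of Table 8.31. If the sponsor intends Grade 2, change Table 8.31 to match.
- In the neutropenia and thrombocytopenia rows of Table 8.51, limit the restart without further reduction to the first occurrence, and refer second occurrences to Table 8.31.
- State the polatuzumab reduction step in Table 8.31. If 1.4 mg/kg is intended, say so there.
- Minor: use the 8.2 withdrawal wording in Table 8.31 for holds over 21 days.

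The cost is a protocol text amendment, with no change to sample size, visits or analysis.

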8.3 Toxicities during Induction Treatment

Table 8.31: Guidelines for Management of Hematologic Toxicities That Occur During Induction Treatment.

Heatment.					
Event	Action to Be Taken				
Grade 3 or	For patients who have had one or no prior venetoclax or polatuzumab vedotin				
4	dose reduction:				
Hematogic	• Withhold study treatment. ¹				
Toxicity ¹	 Administer RBCs or platelets as required. 				
	 If patient has not already initiated G-CSF, initiate prophylactic G-CSF for current and subsequent cycles. 				
	 Resume venetoclax and polatuzumab vedotin at same dose after interruption for 1st occurrence, once the toxicity has resolved to Grade 1 or baseline level 				
	 Resume venetoclax and polatuzumab vedotin at one level dose reduction after interruption for 2nd occurrence, once the toxicity has resolved to Grade 1 or baseline level. Refer to table 8.21 for dose reduction steps. 				
	• For patients who develop platelet count of 20,000/L while receiving LMWH, reduce the dose of LMWH. For patients who develop platelet count of 20,000/L while receiving platelet inhibitors, consider temporarily withholding platelet inhibitors.				
	No more than 2 dose level reductions in venetoclax and				
	polatuzumab vedotin are allowed during induction.				
	 Consider discontinuation of study drug for patients who require withholding study drug for more than 21 days. 				
	For patients who have had two prior venetoclax dose reductions:				
	 Permanently discontinue study treatment. 				
	 For grade 4 thrombocytopenia ≥ 7 days or grade 3 thrombocytopenia with ≥ grade 2 bleeding resume venetoclax and polatuzumab at one dose level dose reduction after the toxicity has resolved to Grade 1 or baseline level 				

(G-CSF) granulocyte colony-stimulating factor; (LMWH) low molecular weight heparin.

¹ Treatment delays apply to all toxicities; dose modifications apply only to toxicities that are considered to be related to any of the study treatment components. Toxicities that occur during the cycle and subside prior to the next cycle should not trigger the suggested dose modifications.

Table 8.32: Guidelines for Management of Non-Hematologic Toxicities That Occur During Induction

Table 8.32: Guide	elines for Management of Non-Hematologic Toxicities That Occur During Induction		
Event	Action to Be Taken		
General guidance for treatment delays and discontinuation	 If study treatment is withheld for 21 days because of a toxicity that is attributable to study treatment, permanently discontinue study treatment. When a treatment cycle is delayed because of toxicity resulting from any component of the regimen, all study treatment should be held and resumed together to remain synchronized. 		
TLS	 Withhold study treatment.^a Correct electrolyte abnormalities, monitor renal function and fluid balance, and administer supportive care, including dialysis as indicated. If symptoms have resolved completely, resume rituximab and hyaluronidase human and polatuzumab at full dose and resume venetoclax at current dose. During venetoclax ramp-up, if venetoclax was withheld for 7 days or less, resume venetoclax at same dose level or at one lower dose level, as determined by the investigator (based on risk assessment, including tumor burden status). Refer to Table 8.21 for dose reduction steps. During venetoclax ramp-up, if venetoclax was withheld for more than 7 days, the dose must be resumed at one lower dose level, with the exception of the first dose (20 mg). Refer to Table 8.21 for dose reduction steps. If resolved within 24 to 48 hours of last dose, resume venetoclax at the same dose. For any blood chemistry changes requiring more than 48 hours to resolve, resume at a reduced dose. Refer to Table 8.21 for dose reduction steps. For any events of clinical TLS, resume at a reduced dose following resolution. Refer to Table 8.21 for dose reduction steps. 		
New-onset neurologic manifestations suggestive of PML AST, ALT, or bilirubin	 Withhold study treatment.^a Consult with a neurologist if PML is suspected. If PML is ruled out, resume rituximab and hyaluronidase human, polatuzumab vedotin and venetoclax at current dose. If PML is confirmed, permanently discontinue study treatment. 		
increase: Grade 3 (or 10x ULN for patients with liver involvement)	 If improvement to Grade 1, resume rituximab and polatuzumab vedotin at full dose and resume venetoclax at next lower dose for current and subsequent cycles per guidelines in Table 8.21. No more than 2 dose level reductions from original dose of venetoclax are allowed during induction. Patients who have had two prior dose reductions should be permanently discontinued. Refer to Table 8.21 for dose reduction steps. Permanently discontinue study treatment for life-threatening liver toxicity. 		
Infections and Infestations; AE: Hepatitis viral	Discontinue therapy and treat hepatitis		

Table 8.32: Guidelines for Management of Non-Hematologic Toxicities That Occur During Induction (cont.)

Event	Grade	Action to Be Taken	
Peripheral Neuropathy	Grade 4	Permanently discontinue polatuzumab vedotin and all other study treatment.	
	Grade 2	1. Delay study treatment. a	
	or 3	2. If improvement to Grade 1 within 21 days, resume study treatment for current and subsequent cycles as follows:	
		a. Resume rituximab or rituximab and hyaluronidase human at full dose	
		b. Resume venetoclax at current dose ^a	
		c. For patients who started at 1.8 mg/kg, resume polatuzumab vedotin at the permanently reduced dose of 1.4 mg/kg;	
Other non-hematologic toxicities (i.e., not described above), excluding alopecia, nausea, and vomiting	Grade 3 or 4	 dose of 1.4 mg/kg; For patients who have had no prior dose reductions: Withhold study treatment.^a If improvement to Grade 1 or baseline, resume rituximab and polatuzumab vedotin at full dose and resume venetoclax at next lower dose ^a for current and subsequent cycles perguidelines. For patients who have had one prior dose reduction: Grade 4 events Permanently discontinue study treatment. Grade 3 events Withhold study treatment.^a If improvement to Grade 1 or baseline, rituximab and polatuzumab vedotin at full dose and resume venetoclax at next lower dose ^a for current and subsequent cycles per guidelines. No more than two dose level reductions from the original dose of venetoclax are allowed during induction. For patients who have had two prior dose reductions: Permanently discontinue study treatment. 	
	Grade 2	 Withhold study treatment.^a If improvement to Grade 1 or baseline, resume rituximab and polatuzumab vedotin, and venetoclax at full dose. 	

IRR-infusion-related reaction; PML-progressive multifocal leukoencephalopathy; TLS-tumor lysis syndrome; ULN-upper limit normal.

^a Treatment delays apply to all events; dose modifications apply only to events that are considered to be related to any of the study treatment components. Toxicities that occur during the cycle and subside prior to the next cycle should not trigger the suggested dose modifications.

8.4 Toxicities during Maintenance Treatment provides guidelines for management of toxicities that occur during maintenance treatment.

Table 8.43: Guidelines for Management of Toxicities That Occur during Maintenance Treatment

Table 8.43: Guidelines for Management of Toxicities That Occur during Maintenance Treatment				
Event	Action to Be Taken			
Hematologic toxicity: Grade 3 or 4	 Withhold rituximab and hyaluronidase human and venetoclax Administer G-CSF for neutropenia per institutional guidelines. Administer RBCs or platelets as required. If improvement to Grade 2, resume rituximab and hyaluronidase human at full dose and resume venetoclax next lower dose (Refer to table 8.21 for dose reduction steps.) Patients who are not eligible for further venetoclax dose reductions should be permanently discontinued. If study treatment is withheld for 21 days, permanently discontinue study treatment. 			
Non-hematologic toxicity: Grade 2	Withhold rituximab and hyaluronidase human and venetoclax If improvement to Grade ≤ 1 or baseline, resume rituximab and hyaluronidase human at full dose and resume venetoclax at next lower dose (Refer to table 8.21 for dose reduction steps). o a for subsequent cycles per guidelines o Patients who are not eligible for further venetoclax dose reductions should be permanently discontinued. • If study treatment is withheld for 21 days, permanently discontinue study treatment.			
Infections and Infestations: Hepatitis Viral	Discontinue therapy and treat hepatitis			

G-CSF granulocyte colony-stimulating factor.

Table 8.44: Prophylaxis and Assessments for Tumor Lysis Syndrome

1 4010 0.77. 1 1	Table 8.44: Prophylaxis and Assessments for Tumor Lysis Syndrome				
	High Risk	Regular Risk			
Definition	 Bulky disease defined as: Any lymph node ≥ 10 cm on the screening CT scan Circulating lymphoma cells Other characteristics deemed by the investigator to confer high risk of TLS 	All other patients not meeting definition of high risk			
Hospitalization	initial dose of venetoclax (See Hospitalization section below)	Not required, but may be hospitalized per discussion with the investigator and Medical Monitor			
Assessments	On the day of the initial visit with administration of venetoclax (Cycle 1, Day 1): Serial vital signs will be recorded • Patients who demonstrate electrolyte changes suggestive of TLS should undergo aggressive management and further monitoring as per standard of care and outlined in Appendix II. • Patients still at risk of TLS before the subsequent dose should receive adequate prophylaxis and monitoring.				

LDH=lactate dehydrogenase; TLS=tumor lysis syndrome Obinutuzumab, rituximab, polatuzumab vedotin, and venetoclax-F. Hoffman-La Roche Ltd Protocol GO29833, Version 4

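### Table 8.31, as printed, tells sites both to stop and to resume at a lower dose in patients with two prior venetoclax reductions; the resume bullet should be limited to patients with fewer than two

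*Combined protocol and SAP*

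**What the plan says.** Section 8.3, Table 8.31, covers Grade 3 or 4 hematologic toxicity during induction and has two blocks.

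- **One or no prior reduction.** Treatment is withheld. After recovery, the first-occurrence rule is "Resume venetoclax and polatuzumab vedotin at same dose after interruption for 1st occurrence" and the second-occurrence rule is "Resume venetoclax and polatuzumab vedotin at one level dose reduction after interruption for 2nd occurrence", with a pointer to Table 8.21. A cap follows: "No more than 2 dose level reductions in venetoclax and" polatuzumab vedotin during induction.
- **Two prior reductions.** The heading is "For patients who have had two prior venetoclax dose reductions". The first bullet is "Permanently discontinue study treatment". The next bullet, for Grade 4 thrombocytopenia of at least 7 days or Grade 3 with bleeding of Grade 2 or worse, is to "resume venetoclax and polatuzumab at one dose level dose reduction after the toxicity has resolved to Grade 1 or baseline level".

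Section 8.2 introduces the dose ladder in Table 8.21 with "The dose of venetoclax may be reduced according to the following dose reduction steps based on the starting dose". The ladder lists venetoclax only and has two reduction steps. In Table 8.32, the liver row says "Patients who have had two prior dose reductions should be permanently discontinued", and the row for other non-hematologic toxicities has the same stop rule.

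**The concern.** The two bullets under the two-prior-reductions heading give opposite instructions for the same patient, and no word such as except or unless links them. A site cannot follow both. One line ends all study treatment. The next re-exposes a patient who has just had prolonged or bleeding thrombocytopenia, at a dose the ladder does not define for someone who started at 400 mg.

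This is an operative dosing rule after a toxicity that carries bleeding risk, so sites should not have to guess. What is at stake is patient safety and consistent dosing across sites, not the statistical design.

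**Working it through.** The plan states no figure on this point, so there is none to reproduce. The check sets the rules side by side and counts reductions.

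**Inputs**

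| Rule | Source | Content |
|---|---|---|
| Cap | Table 8.31 | At most 2 dose-level reductions in induction |
| Ladder, 400 mg start | Table 8.21 | 400 → 300 (Step 1) → 200 (Step 2); no Step 3 |
| Ladder, 200 mg start | Table 8.21 | 200 → 100 → 50 |
| Stop after two reductions | Table 8.31, first bullet | Discontinue |
| Stop after two reductions | Table 8.32, liver row | Discontinue |
| Stop after two reductions | Table 8.32, other non-hematologic row | Discontinue |
| Resume one level lower | Table 8.31, last bullet | Venetoclax and polatuzumab |

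**Count as printed.** Prior reductions + 1 = 2 + 1 = 3, which is above the cap of 2.

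**Dose as printed, 400 mg start.** Two reductions leave 200 mg. The stop line gives 0 mg. The resume line has no dose in the 400 mg row. If a site borrowed the 200 mg row, the dose would be 100 mg, and 100 / 400 = 25% of the starting dose.

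**Count after the fix.** With the bullet limited to 0 or 1 prior venetoclax reduction, the total is at most 1 + 1 = 2, which is within the cap and on the ladder.

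**Alternative layout.** Suppose the last bullet is a stand-alone rule for severe thrombocytopenia.

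1. For a patient with two prior reductions it still meets the stop line and the cap, which point the other way.
2. For a patient with a first occurrence and no prior reduction, the general rule keeps the dose and this bullet lowers it. No exception is worded.

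So both layouts need the bullet's scope stated.

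**Secondary clarifications**

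- *Polatuzumab.* The second-occurrence bullet reduces both drugs and refers to Table 8.21, which has no polatuzumab column. The only reduced polatuzumab dose, 1.4 mg/kg, is given for peripheral neuropathy (Tables 8.32 and 8.51).
- *Table 8.51.* Thrombocytopenia of Grade 3–4 on Day 1 that recovers above 75,000/microliter by Day 7 resumes with no further reduction. Grade 4 that starts on Day 1 and recovers by Day 7 lasts at most 6 days, so it cannot meet the 7-day criterion in Table 8.31. The clear overlap is Day 1 Grade 3 with bleeding of Grade 2 or worse; Grade 4 that began before Day 1 could also fall in it. Neither table says which governs.

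**The case against.** The strongest reply is that the conflict may come from the layout. The table was flattened when the PDF was read, and the last bullet may not belong under the two-prior-reductions heading. The cap, the unqualified stop line, the two-step ladder and Table 8.32 together point to discontinuation. Section 8.2 also withdraws patients delayed more than 3 weeks, apart from exceptional circumstances that may be discussed with the study chair. The tables are titled as guidelines, and Section 8.0 lets investigators make extra reductions.

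Part of this stands. The nesting is uncertain, and a careful reader would probably stop treatment. But a stand-alone bullet still lacks a stated scope, and neither the title nor the discretion in Section 8.0 says when resuming overrides stopping.

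Some stronger readings are tempting but not supported:

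- **The conflict must arise within six 21-day cycles (126 days).** Section 8.2 permits delays of 21 days, and Section 7.2 continues venetoclax after induction until the end-of-induction assessment.
- **It arises at the third toxicity at the earliest.** Section 8.0 allows discretionary reductions, so no minimum number of toxicities follows.
- **Table 8.43 is a further parallel rule for these patients.** It covers maintenance only and does not mention two prior reductions.
- **100 mg appears nowhere in Table 8.21.** It does appear, in other rows. What is missing is a third step for a 400 mg start.

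A deliberate exception for thrombocytopenia cannot be ruled out. It is unlikely: no exception wording appears, and it would keep patients with prolonged or bleeding thrombocytopenia on treatment while other Grade 3–4 hematologic toxicities end it.

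**Conclusion.** The point holds for the table as printed: stop and resume stand under one heading, and the resume line would be a third venetoclax reduction against a cap of 2. It rests on the text as read from the PDF, so confidence in the exact nesting is moderate. The need for a stated scope does not depend on the nesting.

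The size is small. The conflict reaches only patients with two prior venetoclax reductions who then have the specified thrombocytopenia. A footnote to Table 8.31 narrows this further, because toxicity that subsides before the next cycle should not trigger dose modification. The documents give no frequency, so no number of patients can be stated. A reader might infer harm to the trial's inference. The documents do not support that: the decision rules at 16 and 46 evaluable patients, the significance level and the power are unaffected. The polatuzumab and Table 8.51 points are secondary clarifications and do not make the main conflict more serious.

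**What to change.** In Table 8.31:

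1. Move the thrombocytopenia bullet into the block for one or no prior reduction and limit it to patients with fewer than two prior venetoclax reductions.
2. Word it as an explicit exception to same-dose resumption after a first occurrence, with venetoclax one step lower per Table 8.21. The sponsor should first confirm that a reduction at a first such event is intended, since this is a clinical choice.
3. Keep permanent discontinuation as the only action after two prior venetoclax reductions.

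As secondary clarifications, the sponsor should state the reduced polatuzumab dose for hematologic toxicity. It should also say whether Table 8.31 or Table 8.51 governs when Day 1 Grade 3 thrombocytopenia with bleeding recovers by Day 7. Both choices are the sponsor's.

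The cost is amendment wording: one bullet moved, one polatuzumab dose line and one cross-reference. Sample size, decision rules and data collection do not change.
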